1.11. Guidance for Investigator

The investigator is responsible for ensuring the study will be conducted according to GCP, ethical conduct as well as all applicable laws and regulations.

We expect that the study would be granted a waiver from obtaining an informed consent since it is retrospective in nature.

2. OBJECTIVES

The objectives of this study are:

- To evaluate the ability of the Methacetin Breath Test to detect hepatic decompensation events
- To evaluate the relationship between liver Biopsy and clinical outcome and show that the MBT has a better predictive ability of clinical outcome than liver biopsy.

| | |
|--|--|
| Exalenz Bioscience Ltd. | Last update on: April 01, 2015 |
| Protocol: The predictive value of the BreathID, ¹³ C-Methacetin breath test for Hepatic Decompensation; a retrospective analysis | Version Level: 1b |
| Document No.: CSD00074 | Page 12 of 23 |

- To evaluate the ability of the MBT to predict each of the individual liver related complications.

3. ENDPOINTS

3.1. Primary Efficacy Endpoints

The MBT results and the time to hepatic decompensation events:

Hepatic decompensation is defined as the occurrence of at least one of the following events in the time frame between the last ¹³C-Methacetin Breath Test (MBT) to the time of data collection:

1. Death (liver related)
2. Transplantation (cadaveric and living donors)
3. Ascites
4. HE (Hepatic Encephalopathy)
5. Newly diagnosed varices or variceal bleeding
6. SBP (spontaneous bacterial peritonitis)/Sepsis
7. HRS (Hepatorenal syndrome)
8. HCC (hepatocellular carcinoma)
9. Increase in CTP (Child Turcotte Pugh) Score by 3 points
10. Increase in MELD score by 5 points

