1.10. Summary of Overall Risk and Benefits

Since this proposed study is retrospective no adverse events and/or risk associated with the MBT are expected.

The MBT BreathID system consists of the device and ¹³C-Methacetin. The same device but with a different substrate (¹³C-Urea) for the diagnosis of H. Pylori was cleared as a 510(K). The software of the cleared device was upgraded in order to allow the BreathID system to be used in the assessment of liver disease severity. Therefore, the BreathID device does not pose any increased risk to patients participating in this study.

| | |
|--|--|
| Exalenz Bioscience Ltd. | Last update on: April 01, 2015 |
| Protocol: The predictive value of the BreathID, ¹³ C-Methacetin breath test for Hepatic Decompensation; a retrospective analysis | Version Level: 1b |
| Document No.: CSD00074 | Page 11 of 23 |

The ¹³C-methacetin substrate has been used for various breath tests in numerous patients including special populations such as neonatals and pregnant women. To the best of our knowledge no adverse events had ever been reported using ¹³C-Methacetin.

Furthermore, Methacetin is a well known drug that has been available and described in literature for over 30 years and is currently used in medications (such as acetaminophen) for human therapeutic use. No risks have been reported in literature using much higher doses of Methacetin than currently used in the MBT.

During the test procedure, patient contact with the device is through a nasal cannula for collection and analysis of the breath samples. Nasal breathing cannulae are a well-known and proven medical tool having minimum side effects. No discomfort has been reported during prior feasibility studies conducted by Exalenz involving over 400 patients performed with the nasal cannula.

The data analyzed in this study will be used to validate the hypothesis claiming a single ¹³C-Methacetin breath test in chronic liver patients may correlate with liver related morbidity and mortality. This claim had been already been demonstrated in previous studies done by the company, showing a hazard ratio of up to 12 between a single MBT and complications and mortality in chronic patients within one year of the breath test. If such a claim is to be validated, it is expected to influence the clinical practice for such patients preventing the onset of complications and death.

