5. STUDY POPULATION

All subjects previously enrolled into the BreathID pivotal study (HIS-EX-408) and/or the PLT-BID-1108 study and had a valid ¹³C-Methacetin breath test result with or without a valid liver biopsy result at the time of MBT will be included in this retrospective investigation.

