6.3. Safety Observations and Measurements

Hepatic complication events occurring as described in the patient's file from the time of enrollment in the previous pivotal study and the time of this proposed investigation will be recorded.

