8. STATISTICAL CONSIDERATIONS

8.1. Study Design and Objectives

This is a retrospective, multi-center, non-randomized, open label study of the ¹³C-Methacetin BreathID Test (MBT) that will include all patients previously enrolled into the BreathID pivotal study who have performed a valid MBT.

The main objective of the study is to evaluate the ability of the MBT to predict time to hepatic decompensation events.

The secondary objective of the study is show that MBT predictive ability is better than that of liver biopsy/MELD in predicting time to these events.

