8.3. Secondary Endpoint

Histological liver biopsy results (obtained in the initial study) versus clinical outcome at time of current data collection. .

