8.6. Statistical Analyses

All statistical analyses and data presentations, including tabulations and listings, will be performed using the SAS version 9.3 (or higher) software. Statistical tests will be two-sided and the level of significance is 0.05. Nominal p-values will be presented.

Baseline demographics and medical characteristics will be presented in tabular format. The statistical evaluation of baseline characteristics will include all available data.

For continuous variables, the following descriptive statistics will be given: N, Mean, Standard Deviation, Minimum, Median and Maximum values; for discrete variables, the Frequency and Percentage of patients or events will be provided.

For comparison of means (continuous variables), the two-sample t-test or the Wilcoxon rank sum test will be used as appropriate. For comparison of proportions (categorical variables), the Chi-squared test or Fisher's exact test will be used as appropriate.

Kaplan-Meier curves of the time event data will be presented. For comparison of time to event data, the log rank test will be used. Cox regression will be used to estimate hazard ratios, their level of significance and 95% confidence limits.

Risk stratification may be performed by categorizing the MBT into risk groups, for these groups Kaplan-Meier Curves of the time to clinical outcome will be presented for the MBT categories as well as the liver biopsy results to compare predictive value.

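### MBT is dated from the last breath test but biopsy from the initial study, so in any patient with repeat MBTs the MBT-versus-biopsy comparison can be tilted towards MBT

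*Combined protocol and SAP*

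**What the plan says.** The synopsis and sections 3.1 and 8.2 open the event window at the last MBT: "Hepatic decompensation is defined as the occurrence of at least one of the following events in the time frame between the last" MBT and the time of data collection. The secondary endpoint (synopsis, 3.2 and 8.3) is "Histological liver biopsy results (obtained in the initial study) versus clinical outcome at time of current data collection".

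The two markers are meant to be compared. Section 2 aims to "show that the MBT has a better predictive ability of clinical outcome than liver biopsy", and section 8.1 aims to show that "MBT predictive ability is better than that of liver biopsy/MELD in predicting time to these events". Section 8.6 says that risk groups may be formed and that Kaplan-Meier curves will then be "presented for the MBT categories as well as the liver biopsy results to compare predictive value".

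Four other places bear on timing:

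- Section 5 admits patients "with or without a valid liver biopsy result at the time of MBT will be included in this retrospective investigation". It does not say which MBT is meant if there are several.
- Section 6.2.1 records the most recent biopsy, and section 1.7.2 collects repeat biopsies where available. Neither is given a role in an endpoint.
- Section 6.3 says that hepatic events "from the time of enrollment in the previous pivotal study and the time of this proposed investigation will be recorded". Collection therefore starts at enrolment, not at the last MBT.
- Section 1.10 frames the hypothesis around one breath test, citing earlier hazard ratios of up to 12 "between a single MBT and complications and mortality in chronic patients within one year of the breath test".

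No section sets a common index date for MBT and biopsy, a rule for patients with several MBTs, or a limit on the MBT-biopsy interval.

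**The concern.** Section 1.1 states that liver function generally declines before complications appear. A marker read later, closer to the event, therefore tends to predict better even when it is no more accurate. If a patient's MBT is the last of several and the biopsy dates from an earlier visit, part of any MBT advantage may come from the calendar and not from the test.

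The comparison carries weight: section 1.10 says that a better predictive value for MBT would let many patients avoid biopsy. A second consequence concerns events. One that falls between the MBT paired with the biopsy and the last MBT is recorded under 6.3 but lies outside the endpoint window, so the first event counted for that patient may not be the first that occurred.

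**Working it through.** **1. The plan's own figure.** Section 8.5 gives 414 + 165 = 579 as the maximum number of subjects, which reproduces. It is a ceiling that assumes no patient is in both studies.

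**2. The dating rules side by side.**

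| Item | Date used | Where |
|---|---|---|
| Start of event window | Last MBT | Synopsis, 3.1, 8.2 |
| Biopsy as comparator | Initial study | Synopsis, 3.2, 8.3 |
| Biopsy recorded at baseline | Most recent | 6.2.1 |
| Events collected | From enrolment in the earlier study | 6.3 |

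With one MBT per patient, done with the biopsy, the first two dates coincide. With two or more they need not.

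**3. How many patients could have repeats.** The documents give no count. Choosing the last MBT only matters if some patients have several, and eligibility through either study or both allows overlap. If k patients are in both studies, the number of distinct patients is 579 − k and the share with tests in both is k/(579 − k). For k = 0 this is 0%. For k = 165 it is 165/414 = 40%, the most that overlap between studies can produce. Repeats within one study are neither described nor excluded.

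**4. How long the gap could be.** The synopsis dates the MBTs from August 2008 to September 2012, a span of about 4.2 years. This is the testing period for the whole cohort. It caps a within-patient gap but does not estimate one.

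**5. Illustrative size.** The simulation used 579 patients and 200 runs per setting. All other inputs are assumptions:

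- Severity starts as a standard normal and follows a random walk with SD 0.3 (slow) or 0.6 (faster) per root-year.
- Annual hazard is 0.02 × exp(severity), over 26 quarterly steps (6.5 years). This gave about 106 to 133 events.
- Each marker is severity on its reading date plus normal error of SD 0.7, so the two are equally accurate.
- Biopsy is read at entry and MBT at the last test. A repeat MBT occurs 1 or 3 years later, only in patients still event-free.
- Both markers are scored on time from the last MBT.

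Mean C-index difference, MBT minus biopsy:

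| Share with repeat | Slow, 1 y | Slow, 3 y | Faster, 1 y | Faster, 3 y |
|---|---|---|---|---|
| 10% | +0.001 | −0.001 | +0.003 | +0.005 |
| 28% | +0.002 | +0.008 | +0.009 | +0.018 |
| 50% | +0.006 | +0.009 | +0.017 | +0.034 |
| 100% | +0.008 | +0.015 | +0.032 | +0.055 |

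The simulation standard error is 0.001 to 0.002. With no repeats the difference was +0.002 (slow) and −0.002 (faster). With both markers read at a common date it lay between −0.004 and +0.003, as it should for equal markers. At 28% repeats, MBT came out ahead in 51% to 80% of simulated studies, where about 50% is fair.

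**6. The clock.** Put the biopsy-paired MBT at time 0, the last MBT at g and an event at t < g. Section 6.3 records the event and the endpoint omits it. The plan does not say which clock the biopsy curves use. If they start at biopsy while only events after the last MBT count, the interval from 0 to g is event-free by construction.

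**The case against.** The strongest reply is that no document shows a single patient with two MBTs. Section 1.10 speaks of one test, section 5.1.1 asks for a valid result, and 579 is a plain sum. Section 8.5 also calls both parent studies initial, so the biopsy of a patient in both could come from either. If it came from the later one, it might be paired with the last MBT. Section 5 points towards such pairing, and sections 1.7.2 and 6.2.1 show that later biopsies may be on file. Finally, the text fixes the event window; it never states that the last MBT value is the predictor.

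All of this stands as a limit on how much can be claimed. It does not remove the point: the biopsy endpoint is worded the same way in three places, no endpoint uses a later biopsy, and taking the last MBT value as the predictor is the natural reading of a clock that starts there.

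A reader might infer two stronger conclusions that the documents do not support:

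- **A large bias from a gap of about four years in most patients.** Four years is a calendar span, and overlap between the studies cannot exceed 40%, so the 100% row is not a realistic case for that mechanism. In a separate illustrative model with 30% repeats and about 80 events, the tilt was 0.014 to 0.025 against a sampling SD of about 0.033. The plan also names no C-index, so these figures indicate direction and rough scale only.
- **A biased primary analysis.** Starting the clock at the test being evaluated is a legitimate prognostic origin when MBT is assessed alone. The event time lost before it is a design choice.

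**Conclusion.** The point holds in a conditional form. As written, the plan allows MBT to be read later than the biopsy it is compared with, in any patient with repeat MBTs, and the resulting tilt favours MBT. It also leaves collected events uncounted in those patients.

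The size in this cohort cannot be computed. It is zero without repeats and small when they are few. Under the assumed drift and gaps, it reaches about +0.018 in C-index at 28% repeats. The conclusion rests on three things: that some patients have several MBTs, that the last value is the predictor, and that the biopsy precedes it. The wording permits each, but the documents confirm none. This is an inexpensive improvement to a stated objective, not a defect that undermines the study.

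**What to change.** For the MBT-versus-biopsy comparison (8.3 and 8.6):

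- Include only patients with both a valid MBT and a valid parent-study biopsy.
- Define the index MBT as the one performed with that biopsy. If a patient has such a pair in both studies, state in advance which is used.
- Start one clock for both markers at that date and count all events from it, with the CTP and MELD baselines for events 9 and 10 taken at the same date.
- Report the number of patients with repeat MBTs and the distribution of the MBT-biopsy interval.

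The last-MBT origin may stay for the MBT-only primary analysis. Add a sensitivity analysis from the first valid MBT.

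The cost is a wording change and a little more analysis. Parent-study records are already reviewed (6.1, 6.2.1) and events since enrolment are already collected (6.3). The maximum of 579 for the study does not change, although the comparison itself loses patients without a biopsy, whose number is not stated. The MBT advantage over biopsy may look slightly smaller. If there are no repeat MBTs, aligning the dates changes nothing.

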3.2. Secondary Efficacy Endpoints

- Histological liver biopsy results (obtained in the initial study) versus clinical outcome at time of current data collection
- Time to each of the individual events as follows:
 1. Death (liver related)
 2. Transplantation (cadaveric and living donors)
 3. Ascites
 4. HE (Hepatic Encephalopathy)
 5. Newly diagnosed varices or variceal bleeding
 6. SBP (spontaneous bacterial peritonitis)
 7. HRS (Hepatorenal syndrome)
 8. HCC (hepatocellular carcinoma)
 9. Increase in CTP (Child Turcotte Pugh) Score by 3 points.
 10. Increase in MELD score by 5 points .

3.3. Safety Endpoint

No safety endpoint will be evaluated since this is a retrospective study.

| | |
|--|--|
| Exalenz Bioscience Ltd. | Last update on: April 01, 2015 |
| Protocol: The predictive value of the BreathID, ¹³ C-Methacetin breath test for Hepatic Decompensation; a retrospective analysis | Version Level: 1b |
| Document No.: CSD00074 | Page 13 of 23 |

4. STUDY DESIGN

This is a retrospective, multi-center, non-randomized, open label study of the ¹³C-Methacetin BreathID Test (MBT) that will include all patients previously enrolled into the BreathID pivotal study (HIS-EX-408) and/or the PLT-BID-1108 study, that have performed a valid MBT. The information collected in this study will be anonymous.

5. STUDY POPULATION

All subjects previously enrolled into the BreathID pivotal study (HIS-EX-408) and/or the PLT-BID-1108 study and had a valid ¹³C-Methacetin breath test result with or without a valid liver biopsy result at the time of MBT will be included in this retrospective investigation.

5.1. Entry Criteria

5.1.1. Inclusion Criteria (screening visit)

To be eligible for inclusion into this study, the subjects must fulfill all of the following criteria:

- Previously enrolled into a BreathID Methacetin study according to study protocol.
- Has a valid Methacetin breath test result.
- Patient file is available for review.

5.1.2. Exclusion Criteria (screening visit)

Subjects that meet any of the following criteria will not be included in this study:

- a. Patient was not enrolled into the pivotal or PLT studies according to study protocol.
- b. Patient file is not available for review.

6. STUDY PROCEDURES AND ASSESSMENTS

6.1. General Instructions

This study is based on review of patients source file (patient's file) as well as the CRFs gathered from the BreathID Methacetin Breath Test studies (HIS-EX-408 and PLT-BID-1108).

| | |
|--|--|
| Exalenz Bioscience Ltd. | Last update on: April 01, 2015 |
| Protocol: The predictive value of the BreathID, ¹³ C-Methacetin breath test for Hepatic Decompensation; a retrospective analysis | Version Level: 1b |
| Document No.: CSD00074 | Page 14 of 23 |

6.2. Outline of Study Procedures and Assessments

6.2.1. Screening and baseline

Subjects' existing CRFs will be reviewed to identify eligible subjects. The following data will be recorded:

- Demographic data
- Medical history
- History of all prescription or non-prescription drugs, vitamins, and dietary supplements
History of drug and alcohol use.
- Disease history, including date of initial diagnosis, stage of disease , previous treatments and responses
- Status of disease activity
- Concomitant medication and procedures
- MBT results
- Most recent biopsy results if available.

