5. Newly diagnosed varices or variceal bleeding
6. SBP (spontaneous bacterial peritonitis)/Sepsis
7. HRS (Hepatorenal syndrome)
8. HCC (hepatocellular carcinoma)
9. Increase in CTP (Child Turcotte Pugh) Score by 3 points
10. Increase in MELD score by 5 points

Primary Endpoints:

Time to the first occurrence of a hepatic decompensation event (as defined in the primary outcome measures).

Secondary endpoints:

| | |
|--|--|
| Exalenz Bioscience Ltd. | Last update on: April 01, 2015 |
| Protocol: The predictive value of the BreathID, ¹³ C-Methacetin breath test for Hepatic Decompensation; a retrospective analysis | Version Level: 1b |
| Document No.: CSD00074 | Page 5 of 23 |

- Histological liver biopsy results (obtained in the initial study) versus clinical outcome at time of current data collection
- Time to each of the individual events as follows:
 1. Death (liver related)
 2. Transplantation (cadaveric and living donors)
 3. Ascites
 4. HE (Hepatic Encephalopathy)
 5. Newly diagnosed varices or variceal bleeding
 6. SBP (spontaneous bacterial peritonitis)/Sepsis
 7. HRS (Hepatorenal syndrome)
 8. HCC (hepatocellular carcinoma)
 9. Increase in CTP (Child Turcotte Pugh) Score by 3 points.
 10. Increase in MELD score by 5 points

Study Design: Retrospective, multicenter clinical evaluation of patients' outcome initially enrolled (n=414+165=579) into the Exalenz pivotal studies (protocols HIS-EX-408 and/or PLT-BID-1108 respectively). The information collected in this study will be anonymous.

Study Population: A maximum of 579 adult male or female patients enrolled into the Exalenz studies (protocols HIS-EX-408 and/or PLT-BID-1108) who performed a ¹³C-Methacetin Breath Test.

Main Inclusion Criteria: Patient has been tested with the MBT in the past Exalenz pivotal studies protocols HIS-EX-408 and/or PLT-BID-1108 (from August 2008 to September 2012).

Main Exclusion Criteria: Patient had been enrolled into the pivotal study but not included in the final analysis due to conditions / factors interfering with the MBT (i.e. exclusion criteria within the HIS-EX-408 and/or PLT-BID-1108 study).

Statistical Analysis:

Introduction:

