10.3. Data Management

The Investigator or designee will be responsible for recording study data in the paper CRF. It is the Investigator's responsibility to ensure the accuracy of the data entered in the CRFs. A copy of the paper CRF will be kept at site and the original sent for data processing.

The data will then be entered into a validated database. Database lock will occur once quality assurance procedures have been completed.

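### Nothing in the plan stops the site from knowing the breath-test result while it classifies and dates the judgement-dependent primary events

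*Combined protocol and SAP*

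**What the plan says.** Section 6.1 names two sources for one review: "This study is based on review of patients source file (patient's file) as well as the CRFs gathered from the BreathID Methacetin Breath Test" studies. Section 6.2.1 opens with "Subjects' existing CRFs will be reviewed to identify eligible subjects. The following data will be recorded"; its list includes the MBT results and the most recent biopsy.

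For outcomes, section 6.3 records "Hepatic complication events occurring as described in the patient's file from the time of enrollment in the previous pivotal study" onward. Section 10.3 says who writes it down: "The Investigator or designee will be responsible for recording study data in the paper CRF". Section 4 describes the work as follows: "This is a retrospective, multi-center, non-randomized, open label study". Section 8.1 repeats that description.

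The primary endpoint (Synopsis; sections 3.1 and 8.2) is time to the first of ten components, so both event status and event date matter. No diagnostic criteria or dating rules are given for the clinical components. Section 1.1 itself describes ascites and encephalopathy as subjective assessments, contrasts them with the laboratory-only MELD, and lists both among the contributors to CTP.

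The only data check is source data verification by the CRA (section 10.4). No section provides for masking the MBT, a separate abstractor or endpoint adjudication.

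**The concern.** When the person coding an outcome can see the predictor, doubtful cases may be settled in line with it. Several components leave room for this: whether a death was liver related, whether a note amounts to ascites or HE, whether an infection counts as SBP/sepsis, whether renal failure is HRS, and on what date each began.

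The protocol also gives its readers an expectation. Section 1.10 reports an earlier hazard ratio of up to 12 and presents this study as validating the claim.

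At stake is the primary hazard ratio. Recording that depends on the MBT would move it away from 1 if abstractors lean toward the expected result, and more subjects would not correct that. The exposure is also avoidable, because the MBT values come from two completed sponsor studies and the site does not need to handle them again.

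**Working it through.** **Step 1: the sections side by side.**
- Predictor: earlier study CRFs reviewed, MBT result recorded (6.1, 6.2.1).
- Outcome: events recorded from the patient file (6.3).
- Recorder: investigator or designee, on a paper CRF (10.3).
- Safeguard: source data verification (10.4); no masking; open label (4, 8.1).

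No sentence assigns both steps to one person, and none separates them. What is established is that a safeguard is missing.

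**Step 2: a scale for the event count.** The plan gives no power calculation or event target. Its sample size reproduces: 414 + 165 = 579 (8.5). The Synopsis expects 3-5% a year in stable cirrhosis, multiplied by 6, which is 18-30%. Applied to everyone:
- 579 × 0.18 = 104 events
- 579 × 0.30 = 174 events

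These rates are for stable cirrhosis and not all subjects have it, so the counts only set a scale.

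**Step 3: effect on the hazard ratio.** Let J be the share of events that depend on judgement, and s the ratio of recording those events in poor-MBT versus good-MBT patients. Then, approximately,

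HR observed = HR true × [J × s + (1 − J)]

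J, s and the split into two equal MBT groups are assumptions. The plan defines no MBT cut-off, and risk grouping is optional (8.6).

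**Step 4: false-positive rate at a true HR of 1.** With b the factor in brackets, E events and equal groups, z = ln(b) × √E / 2. The two-sided 5% test rejects with probability Φ(z − 1.96) + Φ(−z − 1.96).

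Worked case, J = 0.5 and s = 1.25: b = 0.5 × 1.25 + 0.5 = 1.125. With E = 104, z = 0.1178 × 5.099 = 0.60, giving 0.087 + 0.005 = 9.2%.

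| J | s | Factor b | True HR 2 reads as | False positives, 104 events | False positives, 174 events |
|---|---|---|---|---|---|
| any | 1.0 | 1.00 | 2.00 | 5% | 5% |
| 0.3 | 1.1 | 1.03 | 2.06 | 5.3% | 5.4% |
| 0.5 | 1.25 | 1.125 | 2.25 | 9.2% | 12.1% |
| 0.7 | 1.5 | 1.35 | 2.70 | 33.4% | 50.8% |

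The row s = 1 is what masked abstraction aims for.

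**The case against.** The strongest reply is that the abstractor transcribes and does not diagnose. Events are those already charted during care, and the CRA checks entries against source. Transplantation and a 5-point MELD rise leave little to interpret. This stands, and it confines the concern to classifying, attributing and dating the judgement-dependent components. It does not remove the concern, because source verification confirms that an entry has support in the chart; it does not mask the judgement behind the entry.

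Four stronger readings are tempting, and the documents do not support them.

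- **A reader might infer that one person codes events with the MBT result open.** Section 6.2.1 does not say who reviews the CRFs, and section 10.3 allows a designee. The plan permits this arrangement without stating it.
- **A reader might infer that no planned analysis could reveal the bias.** Time to each individual event is a secondary endpoint (3.2). An MBT association seen for ascites and HE but absent for transplantation and MELD would be a warning sign, though it would not correct the primary result.
- **A reader might apply the error to the whole composite.** With 18% risk in both groups, suppose 10% of event-free poor-MBT patients are coded as events and 10% of true events in good-MBT patients are missed. The proportions are 0.18 + 0.82 × 0.10 = 0.262 and 0.18 × 0.90 = 0.162, and the apparent HR is ln(0.738)/ln(0.838) = 1.72. But 0.082/0.262 = 31% of the poor-MBT events would then be invented, across components that are hard to miscode, and would have to survive source verification. That is an extreme case.
- **A reader might infer that the MBT-versus-biopsy comparison is tilted toward MBT.** Biopsy is on the same list in section 6.2.1, so both predictors are visible under the current plan.

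**Conclusion.** The concern holds as an avoidable gap: event abstraction is not masked to the MBT, and nothing prevents the abstractor from knowing the result. The exposed components are liver-related death, ascites, HE, SBP/sepsis, HRS and the parts of CTP that rest on ascites and HE.

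Bias away from 1 is the expected direction if abstractors expect a poor MBT to predict events; the documents do not show that it will occur. Its size cannot be derived from them. Under the assumed range (J from 0.3 to 0.7, s from 1.1 to 1.5) the hazard ratio is multiplied by about 1.03 to 1.35, which runs from negligible to serious. The change should be made before abstraction starts, because a site that has already seen the values cannot be masked afterwards.

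**What to change.** - **6.2.1:** remove the MBT results and the original-study biopsy result from what the site records. The sponsor sends each site the eligible subject numbers, a valid-MBT flag, the MBT date, and the baseline items needed to judge new events (CTP, MELD, varices status), without MBT values. If the earlier databases lack a baseline item, take it from the patient file.
- **6.3 and 10.3:** require events and dates to be abstracted from the patient file without opening the earlier breath-test CRF. Adjust 6.1 to match.
- **Data handling:** merge MBT and baseline biopsy values from the existing study databases after the event data are locked, using the original subject number or the site's identification log (10.5).
- **4 and 8.1:** amend the open-label description to say that event abstraction is masked to the MBT.
- **8.6:** contrast the less judgement-dependent components already planned (transplantation, MELD rise) with the judgement-dependent ones.

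The cost is protocol wording, fewer CRF items, a sponsor-prepared list per site and one merge. No extra reader is needed.

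The plan should state three limits. An investigator may remember a patient's MBT. Biopsy in the chart cannot be fully masked, so the MBT-versus-biopsy comparison would be masked unequally. Masking at abstraction does not correct differences in surveillance if treating clinicians knew the MBT during follow-up, which the documents do not address.
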